8.2 Recruitment and Training of Research Assistants

Enumerators will be recruited to assist in screening, recruitment and data collection. The research team will engage persons with previous field study experience and knowledge of the local language. The nurse/nutrition officer in charge of nutrition support in the clinic will be requested to assist the researchers in recording blood glucose levels of the T2DM patients. A two day training will be designed by the research team to introduce the study, study objectives and applicable methods to the enumerators. The training will encompass taking of anthropometric measurements, interviewing techniques and data collection procedures, code of ethics, data management and proper interpretation of questions to avoid the error of individual subjectivity during the interview.

Practical demonstrations, discussions and role play will be used to ensure standardization of interviewing skills, taking of body measurements, and will also help in familiarization with the research questions. The enumerators' competence will be assessed by the research team a day after completion of the training session.

8.3 Recruitment and Training of Phlebotomists

Phlebotomists from KEMRI will be engaged. Through a meeting with the research team, the study, study objectives, blood collection procedures, biomarkers for analysis, standard operating procedures (SOPs), biomarker quantification methods, equipment needs and any other practicalities will be reviewed. This will amount to the development of a laboratory analytical plan for this study.

8.4 Pre-testing of the tools

Questionnaires to be used for the studies will be pre-tested before the commencement of the studies. Participant with similar characteristics will be used for the pre-testing.

8.5 Reliability

Other than pre-testing of the questionnaires, training of research assistants on the questionnaire administration and anthropometric measurements will be done. Calibration of anthropometric equipment will be done routinely to enhance reliability. An average of two readings will be used to record anthropometric measurements. Appetite scores will be assessed using Cronbach's alpha. Approved and standardized SOPs will be followed for different procedures in the different studies.

8.6 Ethical Considerations

Ethical clearance will be sought from the African Medical Research Foundation-Ethics & Scientific Review Committee (AMREF-ESRC). A Research permit will be obtained from National Council for Science, Technology and Innovation. Local authority/opinion leaders and Ministry of Health & hospital management will be briefed by the researcher on the intended activities prior to the start of the study. Approval for all data collection procedures and tools will be sought from the aforementioned committee.

Information on the study will be explained to the local administration, hospital administration and study participants in open sessions during outpatient clinic days. The study will be introduced to the hospital management with an introductory letter and approvals obtained. A pre-visit will be made to the hospitals. The T2DM patients will be issued information sheets containing all information pertaining to the study. Consenting individuals will be recruited only after signing of the informed consent.

During recruitment, unique codes will be used for identification and all data obtained from study subjects will be handled with utmost confidentiality. Study documents containing personal information will be stored in a separate repository. In this case, this information will be removed from study documents where possible. Data collected will strictly be used for study purposes only. The process will consider interests of the study participants and will aim to protect their privacy, dignity and integrity. Access to files will be limited to the investigators.

The data collection procedures will have no serious risks to participants. Placement of the catheter will cause only a little discomfort at the site of the needle prick. Necessary care will be taken to stop the discomfort in a short while within the same day. Their participation in this study will enable us assess responses to the new product from the intended (real) or potential consumers. This will be vital to enable product optimization if need be, and in deciding on the use of this product for a food intervention.

For any unforeseen events due to participation in the study, T2DM participants will be immediately referred from the diabetes outpatient clinic to the casualty department of the same health facility for further examinations, treatment and follow up. The participants from JKUAT will be referred to the University hospital.

A lunch meal will be provided to the study participants after the end of the activity. This is considering the participants come for the research early in the morning in a fasted state.

8.7 Quality Control

The research team will be trained and assessed based on standardized methods and tools as in this protocol. Biochemical analysis will be done at the KEMRI laboratories which participate in a series of inter-laboratory calibration exercises to validate analytical results. All equipment will be well maintained and internally calibrated during the entire study period.

9. DATA PROCESSING AND ANALYSIS

9.1 Laboratory Analyses

Biochemical samples will be assessed for blood glucose, lipid profiles, insulin and C-peptide in serum, all in the fasted state.

[figure not shown]
9.2 Glycemic and insulineric tests

Allowable mean within-subject co-efficient of variance (CV) for the reference food is $\leq 30\%$. The laboratory's inter-assay analytical variation on standard solutions should be $< 3.6\%$. The laboratory's minute-to-minute analytical variation in human subjects for 20 or more duplicate measurements of fasting glucose should generally be $< 5\%$. Glycemic and insulineric responses will be obtained from the iAUC (incremental area under the curve). iAUC is calculated by applying the trapezoid rule (sums of the areas of the triangles and trapezoids) [53]. iAUC is reported in millimole minutes per litre. Below is an example to how the iAUC and GI will be arrived at:

Table 2: Sample blood glucose responses to the ingestion of a 50g carbohydrate portion

| Food sample | Time of sampling, min | | | | | | | iAUC |
|----------------------------|-----------------------|-----|-----|-----|-----|-----|-----|------|
| | 0 | 15 | 40 | 45 | 60 | 90 | 120 | |
| Reference food replicate 1 | 4.3 | 6.3 | 7.9 | 5.3 | 4.1 | 4.6 | 4.9 | 114 |
| Reference food replicate 2 | 4.0 | 6.0 | 6.7 | 5.5 | 5.3 | 5.0 | 4.2 | 155 |
| Test food | 4.0 | 5.0 | 5.8 | 5.4 | 4.8 | 4.2 | 4.4 | 93 |

The iAUC for the Reference food replicate 1 = sums of the areas of the triangles and trapezoids A to F obtained after plotting the blood glucose responses at the different time intervals on a graph (Fig. 4).

Key

- c_{Glc} blood glucose
- r' horizontal side of triangle D
- r'' horizontal side of triangle E

Figure 4: Graph of blood glucose responses to the ingestion of a 50g carbohydrate portion over a 2h period

Calculation for GI

- Mean iAUC for the reference food= (iAUC reference food replicate 1+ iAUC reference food replicate 2)/ 2= 135±29 mmol min/l
- The CoV is thus $29/135*100 = 22\%$ (Test condition: CV for the reference food for the group should be $\leq 30\%$).
- iAUC for test food is 93 mmol min/l. For this subject, GI of the test food is thus $93/135*100 = 69\%$.

9.3 Appetite scores

Averages of markings on the VAS for all the participants will be calculated. Descriptive data will be expressed as means and/or standard errors or deviations. Cronbach's alpha will be used to assess validity of the appetite scores. ANOVA, Tukey's significant difference test and Pearsons correlation will be used to analyze the effects of product consumption and composition on appetite scores and to assess the repeatability.

Data will be coded, entered and analysed using either/or SPSS, R, Excel or STATA software.

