7. STUDY DESIGN AND SAMPLING STRATEGY

7.1 Glyceimic index (GI) and glyceimic response study

The GI evaluates the blood-raising ability of equi-carbohydrate portions of different single foods or mixed meals. To assess the GI of the common bean product *in vivo*, 10 healthy volunteers will be recruited. The selection of the number of participants, and the inclusion and exclusion criteria is based on the ISO_26642_2010 standard [53].

The 10 healthy volunteers will be recruited from Jomo Kenyatta University of Agriculture and Technology (JKUAT) and handled at the JKUAT University Hospital.

Inclusion criteria:

- Male or female 18-69 years
- No known food allergies or intolerances
- No prescription medication² (excluding oral contraceptives) known to affect glucose intolerance (e.g. steroids, protease inhibitors, antipsychotics e.t.c.)

Exclusion criteria

- Known history of diabetes mellitus or use of anti-hyperglycaemic medication or insulin
- Alcohol or tobacco use in the evening preceding the test
- Vigorous exercise on the morning of the test
- Undergone major medical/surgical event needing hospitalization within the preceding 3 months
- Presence of disease or drug influencing digestion and absorption of medicine

Glycemic response associated with consumption of the common bean product will be assessed in 10 T2DM patients in Makueni County. The participants will be recruited from the **Makueni Level-5 and Mbooni sub-county hospitals** which run a diabetes outpatient clinic.

Inclusion criteria:

- Male or female aged 18-69 years
- Previously diagnosed with type 2 diabetes
- Consenting to participate

Exclusion criteria:

- Use of prescription medication
- History of eating disorders and irregular eating habits
- Use of tobacco or alcohol
- Females experiencing menstrual period or adverse premenstrual symptoms

For the reference food, we will use either anhydrous glucose powder, 50g or dextrose (glucose monohydrate), 55g. The reference food will be dissolved in 250ml of water and refrigerated for use within 72 hours after preparation. Participants will be fed with an equi-carbohydrate portion of the common bean product to the reference food.

² Stable doses of oral contraceptives, acetylsalicylic acid, thyroxin, vitamins and mineral supplements or drugs to treat hypertension or osteoporosis are acceptable

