7.5 Appetite scores using Visual Analog Scales (VAS)

Appetite scores will be used to assess the satiety power of the test (common bean) product among T2DM participants. The appetite score will be taken on one study day, that is, after consumption of the bean product. Subjective measures of appetite will be taken prior to, and at predetermined time intervals after consumption of the test meal. Appetite score refers to the average between hunger, desire to eat, prospective consumption and a 100-fullness score. The appetite score will be assessed at before and after consumption of test product at time points 0, 15, 30, 45, 60, 90 and 120 minutes. Participants will be given a short questionnaire to assess satiety.

A single vertical mark best expressing the participants' response will be made on an anchored 100 mm VAS scale. The anchor on the left and right will express the most positive and the most negative rating respectively (see Appendix 7). The response will be quantified by measuring the distance between the left anchor and the marking made. The questionnaires will be made as a small brochure booklet showing one question at a time [54][55]. Participants will be asked to remain silent while filling out their VAS. Between evaluations, they will be allowed to read or use their phones. The participants will not be allowed to discuss with each other or refer to previous ratings when filling out the VAS.

Blood draw + Appetite scores

Figure 3: Summary of protocol for the assessment of postprandial glycemic, insulinemic and satiety responses

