11. STUDY LIMITATIONS AND RISKS

Limitations include assessment of one test product. Additionally, when determining the GI and FII, a limitation is in the inter-individual, day-to-day, and even within-day variance in glycemic and insulinemic response to a particular food. For this, we will adhere to recommendations from the ISO 26642:2010 (e.g. testing the reference food twice to reduce day-to-day variability within individuals, follow recommendations as in protocol section 9.2 among other guidelines).

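### The appetite analysis names no result that decides the satiety hypothesis, and Tukey's all-pairs test over the seven rating times is a poor substitute for one pre-specified change from baseline

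*Combined protocol and SAP*

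**What the plan says.** Section 9.3 is the whole analysis plan for appetite. Averages of the VAS marks are to be described, Cronbach's alpha is to be computed, and "ANOVA, Tukey's significant difference test and Pearsons correlation will be used to analyze the effects of product consumption and composition on appetite scores". The same sentence adds repeatability as a further aim. It does not say what the ANOVA factor is, whether participant is in the model, or which comparison matters.

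Section 7.5 fixes the data:

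- Purpose and population: "Appetite scores will be used to assess the satiety power of the test (common bean) product among T2DM participants".
- Occasions: "The appetite score will be taken on one study day, that is, after consumption of the bean product".
- Times: scores are taken "at before and after consumption of test product at time points 0, 15, 30, 45, 60, 90 and 120 minutes", that is, one pre-meal and six post-meal scores.
- Outcome: "Appetite score refers to the average between hunger, desire to eat, prospective consumption and a 100-fullness score".

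Section 7.1 gives the number of patients: "Glycemic response associated with consumption of the common bean product will be assessed in 10 T2DM patients in Makueni County". Section 11 confirms a single product: "Limitations include assessment of one test product". H1 in section 6.1 includes satiety but gives no contrast, time or threshold.

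**The concern.** Tukey's test needs a factor with several levels. There is no second product, composition, group or session in the appetite data, so time is what remains. Applied to time, the test treats a difference between 45 and 60 minutes on the same footing as a difference between 15 minutes and baseline, although only the second kind shows whether appetite fell after the meal.

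Two things are at stake. First, no result is named in advance as the answer. A fall at 15 minutes that has gone by 120 minutes and a fall that lasts to 120 minutes could both be reported as satiety. Glucose and insulin do not have this gap, because section 9.2 reduces each curve to one summary, the iAUC. Second, with about 10 people, the all-pairs test either gives away precision on the comparison of interest or, under another plausible correlation pattern, gives intervals that are too narrow. The plan offers no protection against either.

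**Working it through.** **Inputs.** k = 7 times (7.5). n = 10 (7.1; section 7.5 gives no number of its own, so this is carried over). The documents state no significance level, SD, correlation or power for appetite, so there is no planned figure to reproduce. I assume two-sided 5%, familywise for Tukey. The SD cancels from every ratio below.

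**Counts.** All pairs: 7 × 6 / 2 = 21. Against baseline: 6. Post-meal against post-meal: 6 × 5 / 2 = 15.

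**Critical values.** With participant as a block, error df = 9 × 6 = 54.

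- Tukey: q(0.95; 7, 54)/√2 = 4.331/√2 = 3.062
- Dunnett, six comparisons with baseline, 54 df (simulated): 2.652
- Paired t, 9 df: 2.262
- Single contrast on the pooled error, 54 df: 2.005

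**Equal correlation between times.** Half-widths in units of the within-person residual SD:

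- Tukey, any pair: 3.062 × √(2/10) = 1.369
- One paired baseline contrast: 2.262 × √(2/10) = 1.012. Ratio 1.369/1.012 = 1.35.
- Time-weighted post-meal mean minus baseline. Trapezoid weights over 15 to 120 minutes are 7.5, 15, 15, 22.5, 30 and 15, divided by 105; their squares sum to 0.194. Half-width 2.262 × √(1.194/10) = 0.782. Ratio 1.369/0.782 = 1.75.

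Multiplicity alone accounts for 1.35 (paired t) to 3.062/2.005 = 1.53 (pooled error). The rest of the 1.75 comes from averaging: √(2/1.194) = 1.29, and 1.354 × 1.294 = 1.75. If all six baseline comparisons are kept, replacing Tukey by Dunnett narrows the margin by only 1 − 2.652/3.062 = 13%.

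**Unequal correlation.** Let the total variance be 1 at every time, with correlation b between baseline and each post-meal score and p between post-meal scores. The expected pooled error variance is 1 − (6b + 15p)/21. The variance of the mean-minus-baseline contrast for one person is 1 + p + 0.194(1 − p) − 2b. Each half-width is its critical value times the standard error; for Tukey that is √(2 × pooled variance/10). Familywise error is from 60,000 simulated trials per row with no true change.

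| p | b | Tukey half-width | Paired contrast half-width | Ratio | Familywise error of Tukey |
|---|---|---|---|---|---|
| 0.5 | 0.5 | 0.968 | 0.553 | 1.75 | 5% |
| 0.7 | 0.5 | 0.818 | 0.623 | 1.31 | 6% |
| 0.8 | 0.3 | 0.802 | 0.796 | 1.01 | 10% |
| 0.9 | 0.5 | 0.634 | 0.686 | 0.92 | 12% |
| 0.999 | 0.5 | 0.519 | 0.715 | 0.73 | 14% |

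As post-meal scores move together, the 15 post-meal pairs carry little residual variation. They pull the pooled error down, and Tukey's margin for a baseline pair becomes too small. The narrower interval is then not a gain, because the error rate is two to three times nominal.

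**The case against.** **Time as the factor is an inference.** Section 9.3 speaks of consumption, composition and repeatability, and never of time. That stands, so 21 is the count if Tukey is applied to time, not a number the plan states. With one product on one day, though, there is no second composition and no repeat session to compare.

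**A fixed precision gain.** A reader might infer that Tukey always costs a set amount, say a quarter to a half of the margin. The documents give no correlations to support that. The ratio runs from 1.75 to below 1 in the table, so the gain has no guaranteed lower bound.

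**Inflated error from choosing a time afterwards.** A reader might also infer this. It does not follow: where its assumptions hold, Tukey's test covers every pair, including one picked after seeing the data. The inflation shown above comes from unequal correlation. What the free choice does leave open is which result counts as the answer to H1.

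**Post-meal pairs as irrelevant.** Section 3.4 links satiety to the time until the next eating occasion, and Appendix 3 describes fullness that lasts. How the score moves between 15 and 120 minutes bears on persistence, so these differences deserve display. A mean also cannot tell a brief large fall from a modest lasting one.

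**No comparator.** Appetite is scored after the bean product only. A tighter contrast still shows change after eating this product, not an effect specific to beans. This is right, and it limits what any analysis in 9.3 can claim.

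**Descriptive aim.** The research question in 6.2 is descriptive. But 6.1 states a hypothesis that includes satiety and 9.3 selects inferential tests, so a deciding result is needed.

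**Conclusion.** The point holds in moderate form. Section 9.3 names no result that decides the satiety part of H1, and all-pairs Tukey over time is not well matched to a before-and-after question in about 10 people. Under equal correlation it gives a margin about 1.35 times that of one paired baseline contrast and about 1.75 times that of the post-meal mean minus baseline. Where post-meal scores correlate more with each other than with baseline, the ratio falls to between about 1.0 and 0.7, and familywise error rises to about 10% to 15%. In the first case the paired contrast is better for precision, in the second for validity.

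The figures rest on n = 10, two-sided 5%, equal variances, participant in the model and the correlation patterns shown; none of these is specified for the appetite analysis. The missing deciding contrast rests on no assumption.

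**What to change.** In section 9.3, replace the ANOVA and Tukey wording for appetite with text along these lines:

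- **Deciding contrast.** For each participant, the time-weighted (trapezoid) mean of the section 7.5 composite score over 15 to 120 minutes, minus the time-0 score. Test with a paired t and report the mean change with its 95% CI.
- **Secondary.** The six changes from time 0, including 120 minutes to show persistence, adjusted for multiplicity and with an error term that does not assume sphericity (for example separate paired differences with Holm adjustment).
- **Descriptive.** Differences between post-meal times, shown with the mean curve.
- **Interpretation.** State that, without a comparator meal, the contrast shows change after eating the product and not a bean-specific effect.

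The cost is a few sentences, using data already planned, with no change to visits or procedures. There are three downsides. Comparisons between post-meal times lose formal tests. The six secondary intervals, at 9 df each, may be no narrower than Tukey's. The mean must always be shown beside the time-point changes, because alone it hides the shape of the response.

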10. STUDY FINDINGS COMMUNICATION PLAN

Varied approaches (based on intended audience) will be used to disseminate salient study findings. Findings will be published in peer-reviewed journals and also presented in conferences, research seminars and workshops through oral or poster presentations. Reports will also be shared with Ministries of Health, participating hospitals, LCEFoNS programme platform (hosted by JKUAT website). Letters of thanks to participating hospitals with study updates will be done upon completion of data analysis [57].

Key stakeholders to be included in dissemination of the study include Ministry of Health (MOH), Kenya; Kenya Medical Research Institute (KEMRI) and relevant Non-Governmental Organisations, (participating) T2DM patients, T2DM patient support groups where they exist (at community level this are psychosocial support groups to raise the level of self-care and adherence to treatment), nutritionists/personnel in charge clinics where participants will be recruited from and community leaders.

11. STUDY LIMITATIONS AND RISKS

Limitations include assessment of one test product. Additionally, when determining the GI and FII, a limitation is in the inter-individual, day-to-day, and even within-day variance in glycemic and insulinemic response to a particular food. For this, we will adhere to recommendations from the ISO 26642:2010 (e.g. testing the reference food twice to reduce day-to-day variability within individuals, follow recommendations as in protocol section 9.2 among other guidelines).

12.2 Work plan

| Year 2020 - 2021 | July-Sept 20 | Oct-Nov 20 | Dec 20-Jan 21 | Feb-Mar 21 | Apr-July 21 |
|--|--------------|------------|---------------|------------|-------------|
| Work Package 1: Protocol preparation | | | | | |
| Proposal writing | | | | | |
| Submission of proposal for ethical clearance | | | | | |
| Expected response from ethical body | | | | | |
| Submission to NACOSTI and expected response | | | | | |
| Work Package 2: Metabolic studies | | | | | |
| Review of data collection tools | | | | | |
| Introductory visit to community/local (opinion) leaders/MoH Makeni/JKUAT/JKUAT hospital to inform on research intent | | | | | |
| Recruitment and training of research assistants | | | | | |
| Gathering all data collecting tools | | | | | |
| Pre-test, review of data collection tools, and pre-test report | | | | | |
| Issuance of consent forms and data collection in the various study sites | | | | | |
| Data collection | | | | | |
| Analysis at LANCET and receipt of results | | | | | |
| Work Package 3: Data analysis | | | | | |
| Data compilation and analysis | | | | | |
| Report submission and dissemination (stakeholders) | | | | | |

